### **13.2 Confidentiality of Subjects**

Subject confidentiality will be maintained throughout the clinical study in a way that ensures that study data can always be tracked back to the source data.

Subject information collected in this study will comply with the standards for protection of privacy of individually identifiable health information as promulgated by the U.S. Health Insurance Portability and Accountability Act (HIPAA). All records will be kept confidential, and the subject's name will not be released to persons outside the study site. Subject records will not be released to anyone other than the sponsor or its designees and responsible regulatory authorities when requested. In all cases, caution will be exercised to assure the data are treated confidentially and that the subject's privacy is guaranteed.

PRIME-HF

---

### **13.3 Authorization for Use and Disclosure of Protected Health Information (HIPAA)**

An authorization for use and disclosure of protected health information (PHI) under the HIPAA Privacy Rule will be obtained from every trial subject before enrollment. The investigator is responsible for obtaining subjects' (or their LARs') authorizations and signatures and for explaining the elements of the HIPAA authorization form, if necessary.

The site PI will promptly inform the sponsor of any restrictions on the use or disclosure of any subject's PHI. The site investigator will also promptly inform the sponsor of written revocation of any subject's HIPAA authorization.

### **13.4 Human Subject Protections**

#### **13.4.1 Research Subject Selection and Justification of Exclusions**

There will be no exclusion from participation in the study on the basis of ethnicity or race. Subjects younger than 18 years of age will be excluded from the study, as the target population is adults. Women of childbearing potential will have serum-hCG testing before randomization to avoid potential fetal exposure to ivabradine.

#### **13.4.2 Risks/Discomforts of Study Participation**

This study will evaluate the safety and efficacy of ivabradine following stabilization for acute HF. Oral ivabradine was found to be safe and efficacious in chronic HF patients in the SHIFT trial over a median follow-up of 22.9 mos. In SHIFT, the overall rate of SAEs was similar between the ivabradine and placebo arms; ivabradine was not associated with any evidence of harm over this follow-up period.

### **13.5 Institutional Review Board/Ethics Committee Review**

The appropriate IRB/EC must approve the protocol and informed consent documents, agree to monitor the conduct of the study, and agree to review study progress periodically,

## PRIME-HF

---

at intervals not to exceed 1 year. The investigator will provide the sponsor or designee with documentation that the IRB/EC has approved the study *before* the study may begin.

In addition, the investigator must provide the following documentation to DCRI:

1. IRB/EC annual reapproval of the protocol,
2. IRB/EC approval of revisions to the informed consent documents or any amendments to the protocol. The investigator will provide the sponsor or designee with documentation of all approvals.

### **13.6 Steering Committee**

The Steering Committee will be the primary decision making body of the study and is responsible for its successful completion. The Steering Committee will be comprised of the study principal investigators, the project leader, and selected other investigators with expertise in heart failure and clinical trials.

### **13.7 Data and Safety Monitoring Board**

A data and safety monitoring board (DSMB) will be appointed for the PRIME-HF trial, which will include individuals with pertinent expertise in heart failure and clinical trials. The DSMB will advise the Steering Committee regarding safety concerns for current participants and those yet to be recruited.

---

## 14 Appendices

### Appendix A. Safety Considerations

Similar to the SHIFT study, the following treatments are not allowed at inclusion or during the study:

- Non-dihydropyridine calcium channel blockers (e.g., diltiazem and verapamil)
- Class I anti-arrhythmics (e.g., quinidine, procainamide, lidocaine, phenytoin)
- Strong inhibitors of cytochrome P450 3A4 (CYP3A4), including some macrolide antibiotics (e.g., clarithromycin, erythromycin), cyclosporine, antiretroviral drugs (e.g., ritonavir, nelfinavir), and systemic azole antifungal agents (e.g., ketoconazole, itraconazole)
- Inducers of cytochrome P450 3A4 (CYP3A4) including St. John's Wort, rifampicin, barbiturates, and phenytoin
- Treatments known to be associated with significant prolongation of the QT interval, including sotalol

PRIME-HF

---

**Appendix B. Cardiomyopathy Questionnaire and Patient Global Assessment****Kansas City Cardiomyopathy Questionnaire**

The Kansas City Cardiomyopathy Questionnaire (KCCQ) is a self-administered, 23-item questionnaire developed to provide a better description of health-related quality of life (QOL) in patients with heart failure. It quantifies physical limitation, symptoms, QOL, social interference and self-efficacy. The survey requires 4-6 minutes to complete, and is scored by assigning each response an ordinal value, beginning with 1 for the response that implies the lowest level of functioning and summing items within each domain. Scale scores are transformed to a 0 to 100 range by subtracting the lowest possible scale score, dividing by the range of the scale and multiplying by 100. A clinical summary score will be calculated by combining the functional status with the quality of life and social limitation domains.

**Patient Global Assessment**

A seven category global assessment of clinical status that is completed by the participant will be utilized in the assessment of the composite score. This Patient Global Assessment (PGA) tool consists of the categories of: markedly improved, moderately improved, mildly improved, no change, slightly worse, moderately worse and markedly worse. Participants will be asked to define their status using this tool at specified times during the protocol by marking their current status, relative to the baseline condition. The Patient Global Assessment tool will be prepared in a manner which is simple to read (large print) and will be retained as a source document.

---

## Abbreviations

BB	Beta-blocker
bpm	Beats per minute
ECG	Electrocardiogram
HF	Heart Failure
HR	Heart Rate
IV	Intravenous
KCCQ	Kansas City Cardiomyopathy Questionnaire
LVEF	Left Ventricular ejection fraction
NYHA	New York Heart Association
PGA	Patient Global Assessment

## **1 PURPOSE**

This statistical analysis plan (SAP) reviews the study design and objectives, outlines the types of analyses and data presentations that address study objectives, and describes in detail the statistical methods for safety and efficacy analyses specified in the study protocol (PRIME-HF version 3, of July 19, 2017). Any additional analyses or deviations from the planned statistical analysis will be described in a supplement to this SAP for non-substantive changes, and in an SAP amendment, if the changes are substantive (CT Stats SOP ST-S-005, 5.0, 31Jan2017, V.L).

## **2 STUDY OVERVIEW**

This section summarizes the study objectives and design.

### **2.1 Study Design**

The PRIME-HF study is a multi-center, patient-level, randomized, open-label study with a target of enrolling approximately 450 participants (patients) with reduced LVEF of  $\leq 35\%$  and heart-rate  $\geq 70$  bpm who are being discharged from the hospital following stabilization from acute HF and will be randomized to a treatment strategy of pre-discharge initiation of ivabradine or usual care, involving post discharge initiation of ivabradine.

## **2.2 Study Objectives**

The primary hypothesis of the PRIME-HF study is that, compared with usual care, a treatment strategy of initiation of ivabradine prior to discharge for a hospitalization for acute HF will be associated with a greater proportion of participants using ivabradine at 180 days.

### **2.2.1 Primary Objectives**

To test the primary hypothesis that, compared with usual care, a treatment strategy of initiation of ivabradine prior to discharge for a hospitalization for acute HF will be associated with a greater proportion of participants using ivabradine at 180 days.

### **2.2.2 Secondary Objectives**

To assess the impact of pre-discharge initiation of ivabradine on:

- 1) Heart rate
  - a) Change in heart rate from baseline to 180 days
  - b) Median heart rate at 180 days
- 2) Patient-centered outcomes
  - a) Kansas City Cardiomyopathy Questionnaire ( KCCQ)
  - b) Patient Global Assessment (PGA)

### **2.2.3 Tertiary Objectives**

Tertiary objectives will be to explore the impact of pre-discharge initiation of ivabradine on:

- 1) Other assessments of evidence-based implementation of ivabradine and beta-blockers at 180 days. Evaluations will incorporate data based on whether or not indication status was retained and whether or not an ivabradine prescription was provided.
- 2) Tolerability of ivabradine based on events of interest during study follow-up:
  - a) Symptomatic bradycardia
  - b) Symptomatic hypotension
  - c) Other symptoms leading to ivabradine discontinuation
- 3) To explore barriers to the acquisition of ivabradine.

### **2.3 Sample Size Determination**

For sample size determination, it was assumed that 35% of participants randomized to the usual care arm would be treated with ivabradine at 180 days, and the pre-discharge initiation of ivabradine would increase the use at 180 days to 50%. The usual care event rate is based on investigator estimates of clinical use in the first year following approval by the Food and Drug Administration. At a two-sided Type I error rate of 0.05, 450 participants would provide 85% power to detect a significant difference in the rate of ivabradine use between groups. The original plan was to randomize 450 participants in the study. However, due to enrollment challenges faced in the study, enrollment was stopped after enrolling a total of 104 participants.

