## 1 INTRODUCTION

### 1.1 Background

Heart failure is a major public health issue. More than 5 million Americans have HF and the prevalence is expected to increase as the population ages and survival from coronary, hypertensive, and valvular heart disease improves. Data from randomized clinical trials have established the efficacy of a number of medical and device therapies for patients with chronic HFrEF, but patient outcomes remain poor, especially after a hospitalization for heart failure. The 1-year mortality rate after a HF hospitalization is 20-30%, and this number has been relatively unchanged over the past decade. ***These data suggest that there is an unmet need for novel treatment strategies and supports the assessment of new approaches in the post-acute HF setting.***

There is also wide variation in the implementation of clinical trial evidence into routine practice. Previous data highlight a multi-year gap between the generation of new evidence through clinical trials and the adoption of the data into routine clinical practice. This gap in care translates into many unnecessary deaths and hospitalizations each year for patients with HFrEF. While there are multiple reasons for this quality gap, clinical inertia has most often been noted as a major barrier. Ivabradine have been approved for use in Europe for several years for patients with symptomatic chronic HFrEF (LVEF  $\leq$ 35%) and a heart rate  $\geq$ 75 bpm on guideline-directed medical therapy (or intolerance/contra-indication to beta-blocker use). Ivabradine was recently approved for use in the United States. However, ***no US data exist regarding the potential adoption of ivabradine into routine clinical care.***

Since ivabradine is a newly approved drug, this study also serves as a strategy trial to challenge study sites to explore drug acquisition for a drug that has been proven efficacious to the heart failure population and has been added to 2016 ACC/AHA/HFSA guidelines, however, has not been adopted rapidly into clinical practice. Ivabradine is not being provided for this study. Data are being captured to assess the number of subjects

PRIME-HF

who were able to obtain ivabradine pre and post discharge as well as the barriers to acquisition.

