### **10.2 Sample Size Justification**

We assumed that 35% of participants randomized to the usual care arm will be treated with ivabradine at 180 days, and the pre-discharge initiation of ivabradine would increase the use at 180 days to 50%. The usual care event rate is based on investigator estimates of clinical use in the first year following approval by the Food and Drug Administration. At a two-sided Type I error rate of 0.05, 450 participants would provide 85% power to detect a significant difference in the rate of ivabradine use between groups. This sample size estimate is based on a two-group continuity corrected chi-square test and assumes a 1:1 allocation ratio between the pre-discharge initiation of ivabradine and usual care groups. This sample size estimate allows for 8% missing primary endpoint data.

For the KCCQ overall summary endpoint we have made a conservative assumption of 16 points for the standard deviation. For this measure, the medium and large clinically meaningful differences are 5 and 10 points for the KCCQ overall summary measure, respectively. Allowing for approximately 8% missing data, the proposed sample size of 450 participants provides approximately 90% power to detect a difference of 5 points

---

(medium clinically meaningful difference). The power calculations are based on the two sample t-test with a two-sided Type I error rate of 0.05.

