## **9 ENDPOINT ANALYSES**

### **9.1 Primary Analysis**

The primary analysis will be performed on an intention-to-treat (ITT) basis including all randomized participants. Participant who are not assessed at the 180 day visit due to death or other reasons of early termination, and otherwise medication data not being collected will be coded as failures (ivabradine use=0). The primary analysis will be based on the imputed data. For sensitivity analysis, observed ivabradine use will be used. Given that death is a competing risk of ivabradine use, a competing risk analysis will be performed (see section 11).

The primary analysis will be performed with a logistic regression model, with ivabradine use at 180 days as the binary outcome variable and indicator variables for treatment group main effects

---

 Ivabradine use will be determined from the Ivabradine use pane and will be coded as a “0/1” (no/yes) variable.

and category (0/1) of baseline beta-blocker (BB) use. The treatment effect for the ivabradine at discharge group will be summarized by the odds ratio and associated 95% confidence interval.

Ivabradine use in the ivabradine arm at 180 days is expected to be higher than in the usual care arm.

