### **13.5 Handling of Missing Data**

All efforts will be made to make sure all data needed for the analyses outlined in the SAP are complete. However, it is possible that some data will be missing. Missing data is a common problem in clinical research. It reduces statistical power (the probability that the test will reject the null hypothesis when it is false) and results in biased parameter estimates (Kang, 2013). Outcomes for participants who do not provide data during the 180 day visit will be imputed as failures. Missing heart rate, PGA and KCCQ values will be imputed for the final (180 day) visit using multiple imputation technique if more than 10% of the measures are missing.

It is expected that missing 180 day visit values constitute > 10% of the secondary endpoints (Heart rate, KCCQ and PGA). Thus, multiple imputation (MI) will be performed and presented for the ITT and Treated populations, respectively.

Imputation will be conducted using PROC MI and imputed data analyzed with PROC MIANALYZE in SAS 9.4.

The following variables shall be used in the imputation:

AGE, SEX, RACE, ETHNICITY, WEIGHT, NYHA class, LVEF, and baseline value of the imputed variable) – For NYHA class, WEIGHT and LVEF, baseline values will be used.

RACE shall be recoded to: White, Black and Others (combining American Indian, other, and mixed - as they are of very low frequency)

Results of the imputation shall be presented as the primary result of the secondary endpoints. A total of 25 imputations will be conducted for each imputed value.

Sensitivity analyses will be conducted by analyzing these endpoints with and without imputation.

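### Does the SAP's 85% power for 450 participants need replacing now that enrolment has stopped at 104?

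*SAP*

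**What the plan says.** SAP 2.3 starts from two planning rates. For the control group, "it was assumed that 35% of participants randomized to the usual care arm would be treated with ivabradine at 180 days". For the other group, the authors' expectation was that "the pre-discharge initiation of ivabradine would increase the use at 180 days to 50" percent. At a two-sided 0.05 level it concludes that "450 participants would provide 85% power to detect a significant difference in the rate of ivabradine use between groups". It then describes 450 as the original plan and says that, because of enrolment difficulties, "enrollment was stopped after enrolling a total of 104 participants".

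Protocol 10.2 supplies the remaining design inputs: a continuity-corrected chi-square test, 1:1 allocation, and the statement "This sample size estimate allows for 8% missing primary endpoint data".

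SAP 9.1 says participants not assessed at day 180, deaths included, "will be coded as failures (ivabradine use=0"). It makes that data set the primary analysis and keeps observed use as a sensitivity analysis. The model is logistic regression on treatment and baseline beta-blocker use, summarised by an odds ratio with 95% confidence interval and tested at p<0.05.

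**The concern.** There are two worries.

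- **The sample size.** The SAP's only power figure belongs to a trial more than four times the size of the one that was run. The p<0.05 rule is unchanged, and nothing is said about what 104 participants can detect. A reader who carried 85% forward could take a non-significant primary result as evidence that pre-discharge initiation does not raise use, when the trial would miss the planned effect about two times in three or more.
- **The handling of missing use.** Inflating for 8% missing data treats those participants as lost from the denominator, whereas SAP 9.1 keeps them in as non-users. If the planning rates describe participants with data, this shrinks both rates and the difference between them. The documents also hint that 8% is low. SAP 13.5 says "It is expected that missing 180 day visit values constitute > 10% of the secondary endpoints", and Protocol 1.1 says "The 1-year mortality rate after a HF hospitalization is 20-30" percent. At a constant hazard that mortality implies 1 − 0.80^(180/365) = 10.4% to 1 − 0.70^(180/365) = 16.1% dead by day 180.

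**Working it through.** **Inputs.** p1 = 0.35, p2 = 0.50, two-sided alpha 0.05 (SAP 2.3); continuity-corrected chi-square, 1:1, 8% missing (Protocol 10.2); 104 enrolled (SAP 2.3). The SAP gives no split by arm, so 52 per arm is assumed from the 1:1 ratio.

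**Formula.** With n per arm, d = p2 − p1 and p̄ the mean of the two rates:

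power = Φ{ [√n·d − 1.96·√(2p̄(1−p̄))] / √(p1(1−p1) + p2(1−p2)) }

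The continuity correction replaces d by d − 1/n.

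**Step 1: the plan's figure.** For 35% versus 50%, √(2 × 0.425 × 0.575) = 0.699 and √(0.2275 + 0.25) = 0.691. At n = 207, corrected: [14.387 × (0.15 − 1/207) − 1.370] / 0.691 = 1.040, so power is 85.1%. Then 2 × 207 = 414, and 414/0.92 = 450. The stated figure reproduces exactly.

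**Step 2: 104 participants.** At n = 52, uncorrected: (7.211 × 0.15 − 1.370) / 0.691 = −0.418, power 33.8%. Corrected: −0.618, power 26.8%. With 8% coded as non-users the rates become 0.35 × 0.92 = 0.322 and 0.50 × 0.92 = 0.460, and power is 30.0% uncorrected and 23.4% corrected. Exact binomial enumeration runs about 2 to 3 points higher (25% to 37% across the same cases).

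**Step 3: precision at 104.** If 35% and 50% were observed, the half-width for the difference is 1.96 × √(0.4775/52) = 0.188, about 19 points. The odds ratio is (0.50/0.50)/(0.35/0.65) = 1.86. The standard error of its logarithm is √(1/13 + 1/11.83) = 0.402, so the 95% interval is 0.84 to 4.08. The increase over 35% detectable with 85% power is 29 points (uncorrected) to 31 points (corrected), against 15 planned.

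**Step 4: missing coded as failure at 450.**

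| Reading of 35%/50% and handling of missing | Uncorrected | Corrected |
|---|---|---|
| Participants with data; 8% left out | 87.3% | 85.1% |
| Participants with data; 8% coded as non-users | 85.3% | 83.0% |
| Participants with data; 10% left out | 86.6% | 84.2% |
| Participants with data; 10% coded as non-users | 84.0% | 81.5% |
| Participants with data; 15% left out | 84.6% | 82.0% |
| Participants with data; 15% coded as non-users | 80.6% | 77.8% |
| All randomised, unassessed already counted as non-users | 89.9% | 88.0% |

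The 10% and 15% rows are assumptions, because the documents give no expected missing rate for the primary endpoint beyond 8%. The first six rows also assume missingness equal in both arms and unrelated to use.

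**Step 5: what the SAP does with the 85%.** SAP 2.3 is written in the past tense, names 450 as the original plan and then reports the stop. No section attaches a power figure to 104, links interpretation to 85%, or says a non-significant result will be reported as no difference. SAP 9.1 provides an interval estimate, and SAP 13.2 provides counts and percentages for categorical variables, so use by arm will be visible.

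**The case for a change.** The strongest case for a change is that the authors reopened this paragraph to report the shortfall but left the inference alone. At 104, even an observed result equal to the design target would fail the p<0.05 rule. The hypothesis concerns proportions, yet the treatment effect is summarised only as an odds ratio. Protocol 10.2 also claims about 90% power for a 5-point KCCQ difference, and an unadjusted t-test with SD 16 gives only 33-35% at 48 to 52 per arm. A sentence on power, a risk difference with its interval and a commitment to call a null result inconclusive would cost nothing but wording.

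The arithmetic stands, and so does the omission of any figure for 104. Those additions would be good reporting, but they correct no error. Power is a planning quantity: once recruitment has closed, the confidence interval carries the information, and an interval of 0.84 to 4.08 cannot reasonably be taken as evidence of no effect. An unadjusted risk difference and its interval can be computed from the counts by arm. SAP 2.3 makes no KCCQ power claim, and the planned model adjusts for baseline KCCQ, which would raise the figure (to about 45% at 52 per arm if the baseline correlation were 0.5, an assumption).

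The case about 450 is weaker. SAP 2.3 words the 35% as a share of those randomised, and on that reading the coding rule dilutes nothing. The 8% inflation points to the other reading, so the documents do not settle it. Even then the rule costs about 2 points at 8%, and the uncorrected figure, closer to the planned logistic model, stays at 85.3%. At 10% or more missing, power on that reading does fall below 85% with either test. But the expectation of more than 10% missing in SAP 13.5 concerns heart rate, KCCQ and PGA. Ivabradine use can come from either of two data sets (SAP Appendix 1), and clinic data within 60 days of the window are accepted (SAP 13.1). The 10-16% mortality is an extrapolation from general background to a stabilised, selected population.

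**Conclusion.** No change to the plan is needed. The 85% is right for the 450-participant design and is presented as such, and the stop at 104 is disclosed beside it. What is missing is a restatement for 104: power of about 27-34% with complete data, about 23-30% with 8% coded as non-users, and a 95% half-width of about 19 points. Any competent analyst can supply these, and the reported interval conveys the same message. Stating them would be optional documentation; it would change no test, estimate or decision.

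The figures at 104 assume 52 per arm and the planning rates of 35% and 50%. The 23-30% range also assumes missingness equal across arms and unrelated to use. That missing-as-failure takes power below 85% at 450 is not shown: at 8% missing the answer runs from 83.0% to 89.9%, depending on the continuity correction and an unstated reading of the planning rates. It is also moot for a trial that stopped at 104.
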